#### **4.1.2 Exclusion Criteria**

Patients who meet any of the following criteria will be excluded from study entry:

- Retinitis, poorly controlled seizure disorder, acute confusional state, myelitis, stroke or stroke syndrome, cerebellar ataxia, or dementia that is currently active and resulting from SLE
- Presence of rapidly progressive glomerulonephritis defined by
  - The presence of crescent formation in ≥ 50% of glomeruli assessed on renal biopsy or
  - Sustained doubling of serum creatinine within 12 weeks of screening or
  - The investigator's opinion that the patient has rapidly progressive glomerulonephritis.
- Severe renal impairment as defined by estimated GFR < 30 mL/min or the need for dialysis or renal transplant
- Greater than 50% of glomeruli with sclerosis on renal biopsy
- Treatment with cyclophosphamide or calcineurin inhibitors within the 3 months prior to randomization
- Unstable disease with thrombocytopenia or at high risk for developing clinically significant bleeding or organ dysfunction requiring therapies such as plasmapheresis or acute blood or platelet transfusions
- Lack of peripheral venous access
- Pregnancy or lactation
- History of severe allergic or anaphylactic reactions to mAbs or known hypersensitivity to any component of the obinutuzumab infusion

- Significant or uncontrolled medical disease in any organ system not related to SLE or LN, which, in the investigator's opinion, would preclude patient participation
- Concomitant chronic conditions, excluding SLE, (e.g., asthma, Crohn's disease) that required oral or systemic steroid use in the 52 weeks prior to screening
- Known HIV infection
- Known active infection of any kind (excluding fungal infection of nail beds) or any major episode of infection requiring hospitalization or treatment with IV anti-infectives within 8 weeks of the screening visit or oral anti-infectives within 2 weeks prior to the screening visit
- History of serious recurrent or chronic infection
- History of cancer, including solid tumors, hematological malignancies, and carcinoma in situ (except basal cell carcinomas of the skin that have been treated or excised and have resolved)
- Currently active alcohol or drug abuse or history of alcohol or drug abuse within 52 weeks prior to screening
- Major surgery requiring hospitalization within 4 weeks of randomization (excluding diagnostic surgery)
- Previous treatment with an anti-CD20–targeted therapy within 12 months of randomization
- Previous treatment with a biologic B-cell–targeted therapy (other than anti-CD20) within 6 months of randomization
- Treatment with any investigational agent within 28 days of randomization or five halflives of the investigational drug (whichever is longer)
- Receipt of a live vaccine within 28 days prior to screening
- Intolerance or contraindication to oral or IV corticosteroids
- Aspartate aminotransferase or alanine aminotransferase  $>2.5 \times$  ULN
- Amylase or lipase  $>2 \times$  ULN
- Neutrophils  $<1.5 \times 10^3/\mu\text{L}$
- Positive hepatitis B surface antigen (HbSAg) or hepatitis C serology. Patients who are HBsAg negative and hepatitis B core antibody (HBcAb) positive with no detectable DNA will be allowed into the study but will require regular monitoring of hepatitis B virus (HBV) DNA.
- Hemoglobin  $<7 \text{ g/dL}$ , unless caused by autoimmune hemolytic anemia resulting from SLE
- Platelet count  $<10,000/\mu\text{L}$
- Positive serum human chorionic gonadotropin measured prior to the first obinutuzumab infusion
- Known intolerance to MMF and MPA

## **4.2 METHOD OF TREATMENT ASSIGNMENT AND BLINDING**

The investigator or the investigator's research staff will provide patient eligibility information through the interactive voice/Web response system (IxRS) at randomization. Each patient will be randomized and assigned a unique identification number. As confirmation, the investigator will be provided with written verification of each patient's registration.

Patients will be randomized to receive obinutuzumab or placebo in a 1:1 ratio.

The randomization of patients into treatment and control groups will be managed by a central IxRS vendor by use of a block design. The factors for balancing between the treatment groups will be the following:

- Treatment balance within each race stratum for the following:
  - Region (Afro Caribbean/African American versus others)
  - United States versus non-U.S. sites

Because it is important to maintain blinding to preserve the integrity of the data collected, all laboratory studies of blood specimens, with unblinding potential, will be performed by a central laboratory. Therefore, site personnel and the Sponsor's staff involved with the conduct of the study will not receive unblinded data related to peripheral B-cell counts, PK results, specific immunoglobulin levels, or ADA results during the study, as listed below, until all eligible patients have completed their Week 52 visit.

While PK samples must be collected from patients assigned to the comparator arm to maintain the blinding of treatment assignment, PK assay results for these patients are generally not needed for the safe conduct or proper interpretation of this study. Sponsor personnel responsible for performing PK assays will be unblinded to patients' treatment assignments to identify appropriate PK samples to be analyzed. Samples from patients who are assigned to the comparator arm will not be analyzed except by request (e.g., to evaluate a possible error in dosing).

If unblinding is necessary for patient management (e.g., in the case of a serious adverse event for which patient management might be affected by knowledge of treatment assignment), the investigator will be able to break the treatment code by contacting the IxRS. Treatment codes should not be broken except in emergency situations. If the investigator wishes to know the identity of the study treatment for any other reason, he or she should contact the Medical Monitor directly. The investigator should document and provide an explanation for any premature unblinding (e.g., accidental unblinding, unblinding due to a serious adverse event).

For regulatory reporting purposes and if required by local health authorities, the Sponsor will break the treatment code for all serious, unexpected suspected adverse reactions

(see Section 5.7) that are considered by the investigator or Sponsor to be related to the study drug.

#### **4.3 STUDY TREATMENT**

##### **4.3.1 Formulation, Packaging, and Handling**

###### **4.3.1.1 Obinutuzumab and Placebo**

Obinutuzumab is provided as a single-dose, sterile liquid formulation in a 50-mL pharmaceutical grade glass vial containing a nominal 1000 mg of obinutuzumab (G3 material). The formulated drug product consists of 25 mg/mL drug substance (G3) formulated in histidine, trehalose, and poloxamer 188. The vials contain 41 mL (with 2.5% overfill).

###### **Handling and Storage**

The recommended storage conditions for the obinutuzumab drug product are between 2°C and 8°C and protected from light. Chemical and physical in-use stability for obinutuzumab dilutions in 0.9% sodium chloride (NaCl) have been demonstrated for 24 hours at 2°C–8°C and at ambient temperature and ambient room lighting.

The prepared diluted product should be used immediately. If not used immediately, in-use storage times and conditions prior to use are the responsibility of the user and would normally not be longer than 24 hours at 2°C–8°C. Obinutuzumab should not be frozen or shaken. It should be mixed gently. All transfer procedures require strict adherence to aseptic techniques. An additional in-line filter should not be used because of potential adsorption.

For further details see the Obinutuzumab Investigator's Brochure, pharmacy manual, and local prescribing information.

The placebo employed in this study will be a generic placebo of normal saline, and the double-blinded format will utilize an unblinded pharmacist to enable delivery of obinutuzumab and obinutuzumab placebo.

###### **4.3.1.2 Methylprednisolone and Placebo**

Methylprednisolone and methylprednisolone placebo may be reimbursed by the Sponsor as per local requirements. Local supply of commercially available stock should be used or matching saline solution – prepared by the unblinded pharmacist to maintain the double blind status of the study. For information on the formulation and handling of methylprednisolone, see the pharmacy manual and the local prescribing information for methylprednisolone.

###### **4.3.1.3 Mycophenolate Mofetil/Mycophenolic Acid**

For information on the formulation of and the packaging and handling requirements for MMF and MPA, see the local prescribing information.

#### **4.3.2 Dosage, Administration, and Compliance**

##### **4.3.2.1 Obinutuzumab and Placebo**

Obinutuzumab will be administered by IV infusion at a dose of 1000 mg on Days 1, 15, 168, and 182.

Obinutuzumab must be administered in a hospital or clinic environment where full resuscitation facilities are immediately available and under close supervision of the investigator or designee. Although study drug may be administered on an outpatient basis, patients may be hospitalized for observation at the discretion of the investigator.

See the Obinutuzumab Administration section below for detailed study drug administration instructions for the first infusions (Day 1) and subsequent infusions (Day 15, Day 168, and Day 182) of the two dosing intervals.

Obinutuzumab vials are biologically and chemically stable at 2°C–8°C (36°F–46°F). Do not use beyond the expiration date stamped on the carton. Obinutuzumab should be protected from direct sunlight.

For further details, see the immunology Obinutuzumab Investigator's Brochure and the local prescribing information.

#### **Obinutuzumab Dose and Schedule**

Obinutuzumab will be administered by IV infusion as an absolute (flat) dose of 1000 mg for four infusions on Days 1, 15, 168, and 182. Placebo infusion will be infused in the same volume and on the same scheduled days in the control arm.

#### **Obinutuzumab Preparation**

Obinutuzumab drug product that is intended for IV infusion is prepared by dilution of the drug product into an infusion bag containing 0.9% NaCl to the final drug concentration of 4 mg/mL. Using a 250-mL infusion bag containing 0.9% NaCl, withdraw and discard 40 mL of the NaCl. Withdraw 40 mL of obinutuzumab from a single glass vial and inject it into the infusion bag (discard any unused portion of obinutuzumab remaining in the vial). Gently invert the infusion bag to mix the solution; do not shake.

Administration sets with polyvinyl chloride, polyurethane, or polyethylene as product contact surface and IV bags with polyolefin, polypropylene, polyvinyl chloride, or polyethylene as product contact surface are compatible and may be used. Use of a port or a peripherally inserted central catheter (PICC line) is acceptable.

Do not use obinutuzumab beyond the expiration date stamped on the carton.

#### **Obinutuzumab Administration**

Obinutuzumab should be administered to patients in a clinical setting (inpatient or outpatient) where full emergency resuscitation facilities are immediately available and patients should be under close supervision of the investigator at all times. Do not

administer as an IV push or bolus. After the end of the first infusion, the IV line should remain in place for  $\geq$  2 hours in order to be able to administer IV drugs if necessary. If no adverse events occur after 2 hours, the IV line may be removed. For subsequent infusions, access through an IV line should remain in place for at least 30 minutes from the end of the infusion, and if no adverse events occur after 30 minutes, the IV access may be removed.

Patients should receive prophylactic treatment with acetaminophen (650–1000 mg) and diphenhydramine (50 mg; or equivalent dose of a similar agent) by mouth 30–60 minutes prior to the study drug infusion. Methylprednisolone 80 mg IV must be given 30–60 minutes prior to the start of infusions on Days 1, 15, 168, and 182.

Patients who are administered an antihistamine (e.g., diphenhydramine) for the treatment or prevention of IRRs should be given appropriate warnings prior to the patients' discharge about drowsiness and impairment of ability to drive.

Instructions for administration of obinutuzumab infusions are provided in [Table 2](#) and [Appendix 7](#).

**Table 2 Administration of Obinutuzumab Infusions**

First Infusion (Day 1)	Subsequent Infusions (Days 15, 168, and 182)
Begin infusion at an initial rate of 50 mg/hr. If no infusion reaction occurs, increase the infusion rate in 50-mg/hr increments every 30 minutes to a maximum of 400 mg/hr. If an infusion reaction develops, stop or slow the infusion. Administer infusion-reaction medications and supportive care in accordance with institutional protocol. Resume the infusion at a 50% reduction in rate (the rate being used at the time that the hypersensitivity or IRR occurred) if the reaction has resolved.	If a patient experienced an infusion reaction during the prior infusion, start at the same rate as the first infusion (50 mg/hr) and follow those directions as noted. If the patient tolerated the prior infusion well, begin infusion at a rate of 100 mg/hr. If no infusion reaction occurs, increase the infusion rate in 100-mg/hr increments every 30 minutes to a maximum of 400 mg/hr. If an infusion reaction develops, stop or slow the infusion. Administer infusion-reaction medications and supportive care in accordance with institutional protocol. Resume the infusion at a 50% reduction in rate (the rate being used at the time that the hypersensitivity or IRR occurred) if the reaction has resolved.

IRR=infusion-related reaction.

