**Table 3 Management of Infusion-Related Reactions**

Infusion-Related Symptoms a Grade	Guidance
1–2	Slow or hold infusion. Give supportive treatment b . Upon symptom resolution, may resume infusion rate escalation at the investigator's discretion c .
3	Discontinue infusion. Give supportive treatment b . Upon symptom resolution, may resume infusion rate escalation, at investigator discretion c . Note: If the same adverse event recurs with the same severity, treatment must be permanently discontinued.
4	Discontinue infusion immediately, treat symptoms aggressively, and do not restart drug.

IV=intravenous.

Note: These recommendations do not address life-threatening events, including anaphylaxis, for which all appropriate standard measures (including full resuscitation medications and equipment) must be available and should be used as clinically indicated. For further details see Section 5.1.1.

a Refer to National Cancer Institute Common Terminology Criteria for Adverse Events, v4.0, for the grading of symptoms. This table does not refer to management of immunoglobulin E-mediated allergic reactions.

b Supportive treatment: Patients should be treated with acetaminophen/paracetamol and an antihistamine such as diphenhydramine if they have not been received in the last 4 hours. IV saline may be indicated. For bronchospasm, urticaria, or dyspnea, patients may require antihistamines, oxygen, corticosteroids (e.g., 100 mg of IV prednisolone or equivalent), and/or bronchodilators. For hypotension, patients may require vasopressors.

c Infusion rate escalation after re-initiation: Upon complete resolution of symptoms, the infusion may be resumed at 50% of the rate achieved prior to interruption. In the absence of infusion-related symptoms, the rate of infusion may be escalated in increments of 50 mg/hr every 30 minutes to a maximum rate of 400 mg/hr.

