**Table 6 Guidelines for Management of Specific Adverse Events**

Event	Action to Be Taken
General IRR	

Patients who have pre-existing cardiac or pulmonary conditions should be monitored carefully throughout the infusion and the post-infusion period.

Withholding of antihypertensive treatments should be considered for 12 hours prior to and throughout each obinutuzumab infusion and for the first hour after administration.

Patients at acute risk of hypertensive crisis should be evaluated for the benefits and risks of withholding their anti-hypertensive medication.

Hypersensitivity may be difficult to distinguish from IRRs. If a hypersensitivity reaction is suspected during infusion (e.g., symptoms typically occurring after previous exposure and very rarely with the first infusion), the infusion should be stopped and treatment permanently discontinued.

Patients with known IgE mediated hypersensitivity to obinutuzumab must not be treated.

For additional guidance see Table 3.

Infections: General	

No patient will be enrolled with an active infection or history of chronic or recurring infections.

Patients who develop an active infection during the study will have study drug withheld until the event has resolved.

Patients who require vaccination should be pre-vaccinated 6 weeks prior to receiving study drug.

Vaccination with live vaccine during study is contra-indicated (see Section 4.4.3).

Infections: Hepatitis B	

Hepatitis B screening is required prior to initiation of study drug.

Patients with active or chronic hepatitis B (surface Ag+) will be excluded from the study.

Patients who are HBcAb+ with no detectable DNA will be allowed into the study but will require regular monitoring of HBV DNA. If reactivation is seen, study drug treatment must be withheld.

Patients will be monitored regularly for transaminitis.

Patients with transaminitis will be promptly referred to a hepatologist for evaluation and treatment.

Patients with Hepatitis B reactivation, despite the use of appropriate antivirals, will be discontinued from treatment as outlined in Section 4.6.2.

CSF = cerebrospinal fluid; GI = gastrointestinal; HBcAb = hepatitis B core antibody;

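### Table 2 brings hypersensitivity within its half-rate resume rule, while Table 6 says suspected hypersensitivity should end treatment

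*Protocol*

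**What the plan says.** **Table 2 (Section 4.3.2.1).** The two columns cover the first infusion (Day 1) and the later ones (Days 15, 168 and 182). Both open the reaction rule with "If an infusion reaction develops, stop or slow the infusion". Both then say "Resume the infusion at a 50% reduction in rate (the rate being used at the time that the hypersensitivity or IRR occurred"), provided the reaction has resolved.

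**Table 6 (Section 5.1.9, general IRR row).** This row treats hypersensitivity as hard to tell apart from an infusion-related reaction (IRR). If it is suspected during infusion, "the infusion should be stopped and treatment permanently discontinued". The row describes it as "symptoms typically occurring after previous exposure and very rarely with the first infusion". Patients with known IgE-mediated hypersensitivity to obinutuzumab are not to be treated at all.

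**Table 3 (Section 4.3.2.1).** Footnote c says "Upon complete resolution of symptoms, the infusion may be resumed at 50% of the rate achieved prior to interruption". Footnote a limits the scope: "This table does not refer to management of immunoglobulin E-mediated allergic reactions".

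**Appendix 7.** The half-rate instructions for the first and the subsequent infusions are written for IRRs. They do not name hypersensitivity.

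**The concern.** The two tables give opposite instructions for one event. Under Table 2, a hypersensitivity reaction that has resolved leads to a restart at half the previous rate. Under Table 6, suspicion of hypersensitivity during an infusion should end that infusion and all further study drug.

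Section 4.3.2.1 sends site staff to Table 2 and Appendix 7 for administration instructions, and Table 2 does not mention Table 6. A site that reads Table 2 literally could re-expose a patient for whom the protocol's own safety guidance says treatment should stop. Section 5.1.1 warns that IRRs can look the same as IgE-mediated allergic reactions. The dosing table should therefore not place both under one resume rule.

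**Working it through.** No formula applies, and the plan states no figure to reproduce. The check is a comparison of texts, followed by a search for anything that reconciles them.

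**1. The same event under each table**

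| | Table 2 | Table 6 |
|---|---|---|
| Trigger | An infusion reaction; hypersensitivity is named with IRR where the rate to halve is defined | Hypersensitivity suspected during infusion |
| Action | Stop or slow, then resume at half rate | Stop and discontinue permanently |
| Condition for resuming | Reaction has resolved | None; no resumption |

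For a suspected hypersensitivity reaction that resolves, the actions are incompatible.

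**2. How widespread the wording is**

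- Table 2: named in the first-infusion column and in the subsequent-infusion column, so 2 of 2.
- Other restart texts: Table 3 with footnote c, Appendix 7 first infusion, and Appendix 7 subsequent infusions. None names it, so 0 of 3.

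**3. Which infusions are mainly concerned**

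Infusions are on Days 1, 15, 168 and 182, four in all. Table 6 says these reactions usually follow earlier exposure, so the conflict bears mainly on the second column: Days 15, 168 and 182, or 3 of 4 infusions.

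**4. Does any other text resolve it?**

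- *Table 3, footnote a* excludes IgE-mediated reactions, but from Table 3 only.
- *The notes to Table 3 and Appendix 7* set aside life-threatening events, including anaphylaxis. A suspected hypersensitivity reaction that is not life-threatening falls outside them.
- *Section 4.3.3* recognises that the investigator may decide not to restart, but it concerns an IRR, and a discretionary decision is not permanent discontinuation.
- *Section 4.6.2* lists Grade 4 IRR and recurrent Grade 3 IRR among the reasons to discontinue. It does not list hypersensitivity, so it offers no backstop. No error is claimed in that list.

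**5. Cross-references**

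- Table 2 to Table 6: none.
- Table 6 to Table 2: none. Its pointer ("For additional guidance see") goes to Table 3.
- From the dosing tables to Table 6, two steps: the Table 3 note ("For further details see Section 5.1.1"), then Section 5.1.1 on to Section 5.1.9.

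**The case against.** The best argument on the other side is that Table 2's operative trigger is an infusion reaction. Hypersensitivity appears only in the parenthesis that says which rate to halve. On this reading Table 2 is a general rate schedule, Table 6 is the specific rule, and Table 6 takes over once hypersensitivity is suspected. Appendix 7, which sites are told to read with Table 2, speaks of IRRs only. Table 3 makes resumption discretionary and bars a restart after Grade 4. Section 4.5.9 (ECGs) also treats Section 5.1.9 as the place for decisions on stopping study drug.

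Part of this stands. The position of the word suggests leftover text, and the protocol's intent is fairly clear from Table 6 and from the exclusion of patients with known hypersensitivity. The repetition across columns is one sentence used twice, so it is a single wording problem. The count of other restart texts depends on how they are grouped, although none of them names hypersensitivity however they are divided.

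The conflict remains. A parenthesis that gives the rate from which to resume after hypersensitivity has a purpose only if resumption is contemplated. Reading Table 6 as controlling is sensible, but the protocol does not say so, and site staff should not have to infer it during an infusion. The ECG reference, and a similar one to Section 5.1 under mycophenolate dosing, are not routes from Table 2.

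**Conclusion.** The concern holds. Table 2 and Table 6 give incompatible instructions for a suspected hypersensitivity reaction that resolves, and nothing else in the protocol settles which applies.

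The severity is minor. The conclusion rests on the text alone: Table 2's parenthesis is taken to mean what it says, and Table 6 is taken to express the sponsor's intent. Without an event frequency in the documents, no number of patients at risk can be given. Sample size, power, alpha and the analyses are unaffected. SAP Section 1 records that the Week 52 and Week 104 reports have been issued, so a correction cannot alter blinded infusions already given. It would put the current protocol right and keep the wording from being carried into later documents.

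**What to change.** In both columns of Table 2, delete the words *hypersensitivity or* from the parenthesis, and add: *If hypersensitivity is suspected, do not resume; see Table 6.*

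Section 4.6.2 needs no change. Adding suspected hypersensitivity or confirmed PML to its list would be optional alignment.

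The cost is a wording change in two table cells, with no effect on design or analysis. Staff must still distinguish an IRR from hypersensitivity at the bedside. The edit only makes the dosing table agree with Table 6 once hypersensitivity is suspected.
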